
 
For Cohort 3B: To evaluate the anti-tumor response induced by treatment in participants with mCRPC utilizing solid tumor response criteria.
 
For Cohort 3B: To evaluate the anti-tumor response induced by treatment utilizing immune related response criteria.
 
For Cohort 3B: to evaluate bone metastatic disease outcome in participants with mCRPC.
 
For Cohorts 3B: To estimate the duration of radiographic Progression-Free Survival (rPFS) in participants with mCRPC.
 
To evaluate response rate based on 50% reduction of prostate specific antigen (PSA).
 
To evaluate PSA kinetics.
 
To evaluate trough concentrations of tremelimumab after SC administration at selected doses.
 
To evaluate trough concentrations of PF-06801591 after SC administration at selected doses.
 
To evaluate the anti-drug antibody (ADA) response of tremelimumab after SC administration with the other PrCa VBIR components.
 
To evaluate the ADA response of PF-06801591 after SC administration with the other PrCa VBIR components.
 
	
 
For Cohort 3B: Objective response rate (ORR) and duration of response, as assessed using the Response Evaluation Criteria in Solid Tumors (RECIST) version 1.1 (Appendix 3).
 
For Cohort 3B: Antitumor response and tumor control duration based on total measurable tumor burden as assessed by the Immune-Related Response Criteria Derived from RECIST 1.1 (irRECIST) (Appendix 4).
 
For Cohort 3B: Bone outcome according to Prostate Cancer Working Group 3 (PCWG3) criteria (Appendix 5).
 
For Cohort 3B: Radiographic Progression-Free Survival (rPFS) by RECIST 1.1, irRECIST and PCWG3 Criteria in participants with mCRPC.
 
PSA-50 response rate and duration of response.
 
Baseline and changes from baseline for PSA, PSA velocity, PSA slope and PSA doubling time (PSADT).
 
Trough concentrations after multiple dosing (<math>C_{trough}</math>).
 
<math>C_{trough}</math> after multiple dosing.
 
Incidence and titers of ADA and neutralizing antibodies against tremelimumab.
 
Incidence and titers of ADA and neutralizing antibodies against PF-06801591.
 

CCI	

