#### **4.1.2. Additional Inclusion Criteria for Participants in Part B Expansion Cohort 3B - After Novel Hormone Treatment (enzalutamide or abiraterone)**

16. Prior therapy with a novel hormone therapy (enzalutamide or abiraterone).
17. Testosterone levels  $< 50$  ng/dL.
18. Documented progressive disease and/or local recurrence defined by the following modified PCWG3 criteria:
  - a. PSA progression defined as a minimum of 2 consecutive rising levels, with an interval of  $\geq 1$  week between each determination. For Part B only, the last determination must have a minimal value of  $\geq 0.2$  ng/mL and be determined within two weeks prior to screening.

OR

- b. Measurable disease defined as showing new or progressive metastatic lymph node and/or local recurrence or visceral metastatic disease (with the exception of metastases to the liver) on CT or MRI scans.

OR

- c. Radionuclide bone scan with at least 2 new bone lesions.

For Part B, at least approximately 40% of the participants to be enrolled must have at least 1 measurable lesion as defined by RECIST v1.1.

19. Currently using a GnRH agonist or antagonist (unless surgically castrated).

20. Currently using a GnRH agonist or antagonist (unless surgically castrated).

21. No concurrent treatment with novel hormone therapy.

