#### **Appendix 4. Immune-Related Response Criteria Derived from RECIST 1.1 (irRECIST)**

Increasing clinical experience indicates that traditional response criteria may not be sufficient to fully characterize activity in this new era of targeted therapies and/or biologics.

This is particularly true for immunotherapeutic agents such as anti-CTLA4 and anti-PD-1/anti-PD-L1 antibodies which exert the antitumor activity by augmenting activation and proliferation of T cells, thus leading to tumor infiltration by T cells and tumor regression rather than direct cytotoxic effects. Clinical observations of patients with advanced melanoma treated with ipilimumab, for example, suggested that conventional response assessment criteria such as Response Evaluation Criteria in Solid Tumors (RECIST) and WHO criteria are not sufficient to fully characterize patterns of tumor response to immunotherapy because tumors treated with immunotherapeutic agents may show additional response patterns that are not described in these conventional criteria.

Furthermore, the conventional tumor assessment criteria (RECIST and WHO criteria) have been reported as not capturing the existence of a subset of patients who have an OS similar to those who have experienced CR or PR but were flagged as PD by WHO criteria.

On these grounds, a tumor assessment system has been developed that incorporates these delayed or flare-type responses into the RECIST v1.1 (irRECIST).

For irRECIST, only target and measurable lesions are taken into account. In contrast to RECIST v1.1, irRECIST:

- Requires confirmation of progression by imaging at least 4 weeks from the date first documented, and
- Does not necessarily score the appearance of new lesions as progressive disease if the sum of lesion diameters of target lesions (minimum of 10 mm longest diameter per non-nodal lesion and 15 mm shortest diameter per nodal lesion, maximum of 5 target lesions, maximum of 2 per organ) and measurable new lesions does not increase by  $\geq 20\%$ .

The same method of assessment and the same technique should be used to characterize each identified and reported target lesion(s) at baseline and throughout the trial.

irRECIST is defined as follows:

- Overall immune-related complete response (irCR): Complete disappearance of all lesions (whether measurable or not) and no new lesions. All measurable lymph nodes also must have a reduction in short axis to  $<10$  mm.

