- Overall immune-related partial response (irPR): Sum of the diameters (longest for non-nodal lesions, shortest for nodal lesions) of target and new measurable lesions decreases  $\geq 30\%$ .

- Overall immune-related stable disease (irSD): Sum of the diameters (longest for non-nodal lesions, shortest for nodal lesions) of target and new measurable lesions is neither irCR, irPR, (compared to baseline) or immune-related progressive disease (irPD, compared to nadir).
- Overall immune-related progressive disease (irPD): Sum of the diameters (longest for non-nodal lesions, shortest for nodal lesions) of target and new measurable lesions increases  $\geq 20\%$  (compared to nadir), confirmed by a repeat, consecutive observation at least 4 weeks from the date first documented.

New measurable lesions: Incorporated into tumor burden (ie, added to the target lesion measurements). A lymph node has to be  $\geq 15$  mm in short axis to be a measurable new lesion and its short axis measurement is included in the sum. Up to 2 new lesions per organ and up to 5 new lesions in total can be added to the measurements.

New non-measurable lesions: Do not define progression but preclude irCR.

Overall responses derived from changes in index, non-index, and new lesions are outlined in Table 8.

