4. HYPOTHESES, SAMPLE SIZE AND DECISION RULES

4.1. Statistical Hypotheses

No formal testing of hypotheses will be conducted in this study.

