Selected ad-hoc efficacy analyses (eg, ORR and radiographic PFS) combining participants from Cohorts 7A and 3B may be conducted, as participants in those two cohorts have identical or similar eligibility criteria for study entry and are scheduled to receive the same regimen.

Swimmer plots may be used to display duration of treatment and tumor response at each applicable time point. Waterfall plot for individual tumor size percent change from baseline, and spider plot for individual tumor size percent change from baseline over time may be presented. These plots, if generated, will be presented for RECIST 1.1 and irRECIST separately.

For the rPFS analysis in Part B, the Kaplan-Meier analysis may be performed if deemed necessary. If the Kaplan-Meier analysis is performed for radiographic progression-free survival, an event is defined as the first occurrence of “PD” status by investigator, or death, or a PCWG3 defined bone disease progression, whichever comes first, under RECIST. Time zero for all time-to-event analyses will be defined as the first vaccination on Cycle 1 Day 1. This analysis may be performed for the combined cohorts 7A and 3B. CCI

For duration of response per RECIST and time to response (from the first vaccination date to the time of the first response, CR or PR) in Part B, descriptive statistics will be provided. Kaplan-Meier analysis may be performed if deemed necessary. These analyses may be performed for the combined cohorts 7A and 3B.

PSA kinetics

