Immune-related DC rate (irDCR) is the proportion of patients with irDC.

Immune-related Duration of Response (irDR) is defined, for patients with an immune-related objective response, as the time from first documentation of immune-related objective response (irCR or irPR) to the date of first documentation of irPD (which is subsequently confirmed) or death due to any cause. If a patient has not had an event (irPD or death), irDR is censored at the date of last adequate tumor assessment. The censoring rules for irDR are as described below for irPFS.

$$\text{irDR (months)} = [\text{date of event or censoring} - \text{first date of irOR} + 1]/30.4375$$

Immune-related Time to response (irTTR) is defined, for patients with an irOR, as the time from the start date to the first documentation of immune-related objective tumor response (irCR or irPR) which is subsequently confirmed.

$$\text{irTTR (in months)} = [\text{first date of irOR} - \text{start date} + 1]/30.4375$$

Immune-related Progression-Free Survival (irPFS) is defined as the time from start date to the date of irPD or death due to any cause, whichever occurs first. irPFS data will be censored on the date of the last adequate tumor assessment for patients who do not have an event (confirmed irPD or death), for patients who start a new anti-cancer therapy prior to an event or for patients with an event after two or more missing tumor assessments. Patients who do not have a baseline tumor assessment or who do not have any post-baseline tumor assessments will be censored on the start date unless death occurred on or before the time of the second planned tumor assessment in which case the death will be considered an event.

The censoring and event date options to be considered for the irPFS and irDR analysis are presented in [Table 2](#).

Table 2. Outcome and Event Dates for irPFS and irDR Analyses

Scenario	Date of event/censoring	Outcome
No baseline assessment	Start date	Censored ^a
irPD (subsequently confirmed) or death ≤16 weeks after last tumor assessment or ≤16 weeks after start date	Date of first irPD or death	Event ^b
irPD (subsequently confirmed) or death >16 weeks after the last tumor assessment	Date of last adequate assessment	Censored
Treatment discontinuation due to 'Disease progression' (clinical deterioration without radiological documentation) prior to or within 12 weeks after the assessment of first irPD	Date of first irPD	Event

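### irPFS and irDR in SAP 10.4 have no bone event, so confirmed bone progression followed by new therapy is censored, which lengthens irPFS relative to the RECIST-based rPFS

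*SAP*

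**What the plan says.** The Part B secondary endpoint for Cohort 3B in protocol 2.3, repeated in SAP 6.5, is "Radiographic Progression-Free Survival (rPFS) by RECIST 1.1, irRECIST and PCWG3 Criteria in participants with mCRPC".

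For the RECIST version, SAP 8.1.3 counts investigator-assessed PD, death, "or a PCWG3 defined bone disease progression, whichever comes first, under RECIST". For the irRECIST version, the only visible definition is in SAP 10.4: "Immune-related Progression-Free Survival (irPFS) is defined as the time from start date to the date of irPD or death due to any cause". Table 2 there covers both irPFS and irDR. It censors a participant who starts other cancer treatment before confirmed irPD, and one who has no irPD, at the last adequate assessment.

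The meaning of irPD comes from protocol Appendix 4: "For irRECIST, only target and measurable lesions are taken into account". The definition reads "Overall immune-related progressive disease (irPD): Sum of the diameters (longest for non-nodal lesions, shortest for nodal lesions) of target and new measurable lesions increases" by at least 20% from nadir, with confirmation. It adds: "New non-measurable lesions: Do not define progression but preclude irCR". Appendix 3 follows bone disease as non-target.

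Protocol 4.1.2, criterion 18, admits participants to Cohort 3B on PSA rise, soft-tissue disease or bone scan, and requires only that "at least approximately 40% of the participants to be enrolled must have at least 1 measurable lesion".

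**The concern.** In this population bone is a main site of metastasis; protocol 1.3.1 says most metastatic lesions are in bone and lymph nodes. A progression-free endpoint that cannot register bone progression treats a man who has just progressed there as progression-free. If he then changes therapy, it removes him from the risk set at that point.

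The consequence lies in interpretation. SAP 8.1.3 warns that conventional response and PFS measures can be unreliable for cancer vaccines. A reader who sees irPFS longer than rPFS will naturally take the gap as delayed immune benefit, although part of it would come from the missing bone event. Protocol 3.5 bases the recommended phase 2 dose on the totality of evidence, including efficacy, so the comparison may carry weight even without a test.

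**Working it through.** The documents give no irPFS median, event count or power, so there is no stated figure to reproduce. The check is of definitions, followed by an illustration of size.

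**1. Same finding under the two rules**

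| Finding | rPFS under RECIST (SAP 8.1.3) | irPFS / irDR (SAP 10.4, protocol Appendix 4 and its Table 8) |
|---|---|---|
| Measurable sum up 20% or more | event | event once confirmed |
| Sum unchanged, PCWG3 bone progression | event | no event; scored irSD |
| Sum down 30%, PCWG3 bone progression | event | no event; scored irPR |
| Sum down 100%, bone disease persists unchanged | no event | no event; irPR, not irCR |
| No target lesion, PCWG3 bone progression | event | no event; percentage change undefined |
| New measurable soft-tissue lesion | event | enters the sum; how a 20% rise applies to a zero baseline is not stated |
| Death | event | event, but censored if more than 16 weeks after the last assessment or after a change of therapy |

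**2. Path of a bone progressor in Table 2.** With bone progression and no confirmed irPD, starting new therapy leads to the censoring row. The row for stopping treatment because of clinical progression does not help him, because it takes its event date from a first irPD.

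**3. How many could be affected.** 18 × (1 − 0.40) = 10.8, so at the protocol's floor up to about 11 of 18 lack a measurable lesion. This bounds bone-only disease from above, since entry on PSA alone, or with nodes of 10 to 14.9 mm, also gives non-measurable disease.

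**4. Size.** Assume that time to first progression or death is exponential with median M, that a fraction b of these first events are bone progressions each followed by a therapy change, and that site is independent of time. Censoring those events leaves a hazard of (1 − b) × ln 2 / M, so the Kaplan-Meier median tends to M / (1 − b).

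Let 10% of first events be deaths, n the share without measurable disease, and f1 and f2 the bone share of progressions in those without and with measurable disease. Then b = 0.9 × [n × f1 + (1 − n) × f2]. Only the upper bound of 0.6 on n comes from the documents.

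- Milder: n = 0.4, f1 = 0.7, f2 = 0.2. b = 0.9 × (0.28 + 0.12) = 0.36. M = 6 gives 6 / 0.64 = 9.4 months; M = 4 gives 6.3.
- Stronger: n = 0.6, f1 = 0.9, f2 = 0.3. b = 0.9 × (0.54 + 0.12) = 0.594. M = 6 gives 6 / 0.406 = 14.8 months; M = 4 gives 9.9.
- Events with M = 6 and a 24-month cut-off: 18 × (1 − 1/16) = 16.9 if bone counts, against 16.9 × 0.64 = 10.8 (milder) or 16.9 × 0.406, about 7 (stronger).

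Simulation of the same set-up gives these medians.

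**5. Extreme case.** Suppose nobody dies, every progression without measurable disease is in bone and leads to a switch, and none of the others progress in bone. At a 40% measurable share the formula gives 6 / 0.4 = 15.0 months. With 8-weekly scans (56 / 30.4375 = 1.84 months apart) and cohorts of 18 with 7 measurable, the typical simulated Kaplan-Meier median is 18.4 months. It is 11.0 at a 60% share and 9.2 at 80%, against 7.4 when every progression counts. These values sit on the scan grid, so a change of one scan moves them by 1.84 months.

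**The case against.** The strongest reply is that bone is measured elsewhere by design. PCWG3 bone progression is an event in rPFS, which SAP 4.3 calls the key supportive efficacy endpoint, and bone outcome is a Cohort 3B endpoint of its own. The endpoint line names three criteria without saying that each must contain the others, and irPFS appears by name only among the Part A exploratory endpoints. The SAP also states that "No formal testing of hypotheses will be conducted in this study"; safety is primary and RECIST ORR is the main efficacy endpoint. All of this stands, and it lowers the severity. It does not remove the upward shift in irPFS or the invitation to compare it with rPFS.

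Text is redacted beside the rPFS definition and within SAP 10.4, and SAP 10.3 leaves PFS and rPFS censoring to a programming specification not shown. A bone rule could sit there. The visible irPFS definition and Table 2 are explicit, however, and contain none.

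The size is uncertain. Protocol 3.1 encourages participants to stay on treatment for at least 24 weeks before removal for progression, so not every bone progressor will be censored at the scan that shows it. If 70% rather than all of the progressions in the 60% without measurable disease are in bone, b = 0.42 and the extreme case falls from 15.0 to 6 / 0.58 = 10.3 months.

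Several stronger readings are tempting, and the documents do not support them:

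- *Bone-only participants can never progress under irRECIST, so 11 of 18 cannot have irPD.* They cannot progress on bone findings. A new measurable lesion enters the tumor burden, and death is an irPFS event.
- *irRECIST response ignores bone.* irCR requires non-measurable lesions to clear as well. Only irPR and irSD can stand despite bone progression.
- *Protocol 6.4.1 makes bone progression irPD.* It gives a bone-scan confirmation interval inside a treatment-withdrawal rule and defines no endpoint.

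**Conclusion.** The point holds for irPFS and irDR. On the visible text neither has a bone component, and a bone progressor who changes therapy before confirmed irPD is censored because he progressed. The direction is clear: irPFS is lengthened relative to rPFS for a reason unrelated to immune-type response.

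The amount is not known. It depends on the measurable-disease share in Cohort 3B, the site of progression and the rate of therapy change, none of which the documents give. For an assumed true median of 6 months the illustrations run from about 9 months (comparator 6.0) to about 18 months (scan-based comparator 7.4). The upper end is a worst case, not an estimate. Severity is moderate.

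**What to change.** In SAP 10.4, define the irPFS and irDR event as the first of confirmed irPD, bone progression confirmed per protocol Appendix 5 (dated at the first scan showing it), or death. Add the matching row to Table 2, and state that it takes precedence over censoring at a later change of therapy. In the illustrations this returns the median to the comparator value.

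Leave irBOR and irORR as protocol Table 8 has them, since scoring bone progression as irPD there would override the protocol. Label them as measurable soft-tissue response and show them beside the PCWG3 bone outcome.

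The cost is SAP wording and one derivation on bone-scan results already collected. The downside is that irPFS becomes shorter and closer to rPFS.

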12. **Coagulation:** Should include Prothrombin Time (PT) or International Normalized Ratio (INR) and Partial Thromboplastin Time (PTT). Samples will be analyzed locally.
13. **Cardiac Troponin:** For participants undergoing screening, circulating levels of cardiac Troponin-I (cTnI) must be measured and found to be within the normal reference range within 28 days before study entry, preferably using the central laboratory kits provided. See [Section 7.1.7](#) for full details.
14. **Urinalysis:** Dipstick is acceptable. Microscopic analyses if dipstick abnormal. Samples will be analyzed locally.
15. **Triplicate 12 leads ECGs:** At each time point, three consecutive 12-lead ECGs will be performed approximately 2 minutes apart to determine mean QTcF interval. If the mean QTcF is prolonged (>500 msec), the ECGs should be re-evaluated by a qualified person at the institution for confirmation. Additional triplicate ECGs may be performed as clinically indicated.
16. **Registration:** Participant number and dose level allocation operated by Pfizer Inc.
17. **Investigational Product Administration:** Treatment to be administered after all other assessments required on that day have been performed.
18. **Tumor Assessments:** Tumor assessments will include all known or suspected disease sites. Screening images may be obtained within 5 weeks of registration. Imaging obtained as part of standard of care but within 28 days (-7 days) of registration may be used for screening assessment. Imaging may include chest, abdomen and pelvis CT or MRI scans or bone scans. Bone scans will be performed at baseline if disease is suspected and on-study as appropriate to follow disease. Baseline central nervous system (CNS) imaging is not required with the exception of symptomatic participants to rule out CNS metastases. CT or MRI scans, as well as bone scans, when indicated, are to be done every 8 weeks ( $\pm$  5 days) with the first one to occur 8 weeks after C1D1 until disease progression that requires new treatment modality, permanent discontinuation, or death. Disease progression will be confirmed with two consecutive timepoints at least 4-6 weeks apart in the absence of rapid clinical deterioration. Tumor assessment should be repeated at the End of Treatment visit if more than 6 weeks have passed since the last evaluation. **CCI** [REDACTED]  
[REDACTED]  
[REDACTED]

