New anti-cancer therapy prior to confirmed irPD	Date of last adequate assessment before anti-cancer therapy is given	Censored
irPD not confirmed or no irPD	Date of last adequate assessment	Censored

^a However if the patient dies ≤8 weeks after start date the death is an event with date on death date

^b irPD is also considered to be confirmed if the patient dies within 12 weeks after the initial documentation of irPD

The analyses for irBOR, irOR, irDR, irDC, irTTR will follow the methodology outlined for the RECIST 1.1 endpoints as follows

- irOR will be summarized but no formal test of hypotheses will be performed (only 95% CIs will be reported)
- irBOR, irOR, irDC, irDR, irTTR and irPFS will be summarized as described in Sections xx, for RECIST endpoints but irDR and irPFS will be analyzed using the censoring rules described in Table 2.

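### SAP 10.4 Table 2 can censor a confirmed irPD found after one missed scan, because its 16-week limit ignores the ±5-day scan window, while the irPFS text censors only after two or more missed assessments

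*SAP*

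**What the plan says.** The protocol's Schedule of Activities for the expansion cohorts (footnote 18) states that "CT or MRI scans, as well as bone scans, when indicated, are to be done every 8 weeks", with a window of ± "5 days) with the first one to occur 8 weeks after C1D1 until disease progression". The maintenance schedule repeats the 8-week interval and the 5-day window.

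SAP Section 10.4 gives two rules for events that follow a gap in scanning.

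- **The irPFS definition in the text** censors at the last adequate assessment "for patients with an event after two or more missing tumor assessments".
- **Table 2** censors "irPD (subsequently confirmed) or death >16 weeks after the last tumor assessment", and its event row covers "irPD (subsequently confirmed) or death ≤16 weeks after last tumor assessment or ≤16 weeks after start date".

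Both endpoints follow the table. Of duration of response the SAP says that "The censoring rules for irDR are as described below for irPFS", and the section closes by stating that "irDR and irPFS will be analyzed using the censoring rules described in Table 2".

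**The concern.** The text counts missed assessments and the table counts weeks. The two agree only if the number of weeks separates one missed scan from two. Sixteen weeks is twice the 8-week interval, so it falls on the planned day of the first scan after a single missed one. A scan one day late relative to the previous one, but inside the allowed window, moves a confirmed irPD from event to censored and dates it back about 16 weeks.

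Radiographic PFS by irRECIST is a Part B secondary endpoint for Cohort 3B, which has 18 patients (SAP 6.5 and 4.3). In a cohort that small, one or two reclassified progressions can visibly move a Kaplan-Meier curve. Censoring a progression at the earlier scan raises the curve from the date of that progression onward, although between the two scan dates it may be marginally lower because the risk set is one smaller. Two programmers, one following the text and one the table, could also report different results from the same data.

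**Working it through.** **Inputs from the documents.** Interval 8 weeks = 56 days. Window ±5 days, with the first scan 8 weeks after C1D1. Table 2 limit 16 weeks = 112 days, where 112 or less is an event and more than 112 is censored. Text rule: censor after two or more missing assessments.

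**Input assumed.** The documents do not say how actual scan days fall within the window. The base case takes each whole day from −5 to +5 as equally likely.

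**1. The table's limit.** 2 × 56 = 112 days = 16 weeks. This reproduces the SAP's figure and shows that it contains no allowance for the window.

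**2. Gap after one missed scan.** Let d1 and d2 be the deviations of the last scan and of the scan that finds irPD. With scans anchored to C1D1, gap = 112 + d2 − d1, so the range is 112 ± 10 = 102 to 122 days. If only one scan varies, the range is 107 to 117 days.

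**3. Gap after two missed scans.** Gap = 168 + d2 − d1, range 158 to 178 days.

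**4. Share of irPD after one missed scan that Table 2 censors.** Both scans varying uniformly: 55 of the 121 pairs have d2 > d1, so P(gap > 112) = 55/121 = 45.5%. One scan varying: 5/11 = 45.5%. The text would censor none of these.

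**5. Sensitivity to the timing assumption.**

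| Scan-day timing | Censored share |
|---|---|
| Exactly on schedule | 0% |
| Extra 20 / 40 / 60% probability on the planned day, both scans vary | 44 / 38 / 29% |
| Same, one scan varies | 36 / 27 / 18% |
| Uniform over the window | 45.5% |
| Second scan shifted by a mean of −2 to +2 days, SD 2.5 | 17% to 71% |

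Under any symmetric timing the share is (1 − P(gap = 112))/2, so 50% is a ceiling. With asymmetric timing any value from 0 to 100% is possible.

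**6. Deaths.** Suppose the last scan was on its planned day. A death after one missed scan and before the second is due falls on days 57 to 112, and Table 2 counts it as an event: 0% censored. If the second scan counts as missed only when its window closes on day 117, and deaths are uniform over days 57 to 117, the censored share is 5/61 = 8%.

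**7. Limits that separate one missed scan from two.** For scan-detected irPD, any limit from 122 to 157 days censors 0% after one missed scan and 100% after two. At 112 days the figures are 45.5% and 100%. At 17 weeks (119 days) they are 6/121 = 5.0% and 100%.

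**The case against.** The best defence is that 16 weeks is simply two 8-week intervals. On nominal days the table does match the text, because a gap of exactly 112 days counts as an event. The disagreement arises only for in-window scans that come late relative to the previous one.

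The practical effect may also be small. It needs a patient to miss exactly one scan and then have confirmed irPD at the next, and the documents give no basis for estimating how often that happens. irRECIST uses only target and measurable lesions (protocol Appendix 4). The Part B requirement for measurable disease is at least approximately 40% of participants (protocol 4.1.2); 40% of 18 is about 7 patients, as a floor. The SAP states that "No formal testing of hypotheses will be conducted in this study", and Kaplan-Meier analysis of rPFS is optional (SAP 8.1.3).

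All of this stands, and it limits the consequence. It does not reconcile the two rules. The COVID-19 provision in SAP 10.3 does not help either, since it addresses patients with two or more missed assessments.

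A reader might infer that about half of all events after a single missed scan are lost. The documents do not support that. The 45% rests on an assumed distribution and applies only to irPD found on a scan. If deaths make up 25% of events after one missed scan, the censored share is 0.75 × 5/11 = 34%, or 36% after adding 0.25 × 5/61. At 50% deaths it is 23% to 27%.

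**Conclusion.** The inconsistency is real. Table 2, which the SAP makes operative for irPFS and irDR, can censor a confirmed irPD found at a compliant scan after one missed assessment, and the irPFS text would count that irPD as an event. The size is conditional: about 45% of such irPD if scan days are uniform over the window, 0% if scans are exactly on schedule, and at most 50% under any symmetric timing. The number of patients affected is unknown.

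Two stronger readings should be resisted. One is that deaths are wrongly removed: a death more than 112 days after the last scan normally follows two scans that were due, so table and text nearly agree. The other is that irPFS is materially overstated: nothing in the documents quantifies this, and the endpoints are descriptive. The point is worth correcting because the two rules conflict and the correction is cheap.

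**What to change.** In the event and censoring rows of Table 2, replace the condition of 16 weeks after the last tumor assessment with a count of missed scheduled assessments: event if fewer than two were missed, censored if two or more. State when an assessment counts as missed, for example when its +5-day window closes.

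If a day limit is kept for scan-detected irPD, it should include the scan window; any value from 122 to 157 days works. Do not apply such a limit to the whole row. A 122-day limit would turn deaths on days 113 to 122 into events even where two due scans had been missed, which the text censors. Leave the clause of 16 weeks from the start date tied to the second planned assessment, as the text has it.

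The cost is an edit to two table rows and the matching program specification, with no effect on trial conduct. irPFS and irDR may become slightly less favourable.

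### SAP 10.4 gives conflicting irPFS rules for a participant with no baseline scan who dies after week 8 and by week 16: an event under the text and Table 2 row 2, censored at the start date under row 1 with footnote a

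*SAP*

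**What the plan says.** Three statements in SAP 10.4 bear on the same death.

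- **Text of the irPFS definition.** Participants lacking a baseline assessment, and those lacking every later one, have their irPFS time censored at Day 1. One exception is made: "unless death occurred on or before the time of the second planned tumor assessment in which case the death will be considered an event". It covers both groups alike.
- **Table 2, row 1.** The scenario is "No baseline assessment" and the outcome is censoring at the start date. Footnote a, attached to this row only, adds: "However if the patient dies ≤8 weeks after start date the death is an event with date on death date".
- **Table 2, row 2.** The scenario "irPD (subsequently confirmed) or death ≤16 weeks after last tumor assessment or ≤16 weeks after start date" is an event, dated at the first irPD or death.

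The end of SAP 10.4 directs that irPFS and irDR follow the Table 2 rules, so footnote a is operative. Time zero is set in SAP 8.1.3: "Time zero for all time-to-event analyses will be defined as the first vaccination on Cycle 1 Day 1". The scan timetable is in the tumor assessment footnote to the protocol's Schedule of Activities for the expansion cohorts. The interval is 8 weeks, give or take 5 days, and the series starts "with the first one to occur 8 weeks after C1D1".

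**The concern.** The same participant can be a failure or contribute nothing, depending on which line of SAP 10.4 the programmer follows. The irPFS definition counts death from any cause as an event, so a rule that censors a known death at time zero works against the endpoint it serves.

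Radiographic PFS by irRECIST is a Part B secondary endpoint for Cohort 3B (SAP 6.5). SAP 10.3 leaves the PFS/rPFS censoring rules to a programming specification, so Table 2 is the only tabulated censoring scheme in the SAP. The study is open label and the sponsor's team reviews data throughout (SAP 3). If the conflict remains, someone may have to choose between the readings with the outcome in view.

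**Working it through.** **Inputs**

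- Start date: Cycle 1 Day 1 (SAP 8.1.3).
- First on-study scan: week 8. Interval: 8 weeks, ±5 days (protocol, Schedule of Activities for the expansion cohorts).
- Cut-offs: second planned assessment (SAP 10.4 text), 8 weeks (footnote a), 16 weeks (Table 2 row 2).
- Cohort 3B size: 18 (protocol 3.1.2).

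**Step 1. Put the text's cut-off in weeks.** Second planned assessment = 8 + 8 = 16 weeks, or 112 days after Cycle 1 Day 1, with a scan window of 107 to 117 days. This reproduces the 16-week figure in Table 2 row 2.

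**Step 2. Apply each rule to a participant with no baseline scan who dies without irPD.**

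| Death | Text | Row 1 + footnote a | Row 2, start-date limb |
|---|---|---|---|
| up to week 8 | event | event | event |
| after week 8, up to week 16 | event | **censored at start** | event |
| after week 16 | censored at start | censored at start | does not apply |

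The text and footnote a disagree only in the middle line. Within Table 2, rows 1 and 2 also give opposite answers there.

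**Step 3. Apply them to a participant with a baseline scan but no post-baseline scan.** Row 1 and footnote a do not apply. The text and row 2 both give an event up to week 16, so there is no conflict.

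**Step 4. Size of the effect.** Assume one disputed death and no other censoring. Let *n* be the cohort size and *e* the number of events up to and including this death.

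- Death counted: irPFS = (n − e)/n.
- Death censored at Day 1: irPFS = (n − e)/(n − 1).
- Difference: (n − e)/[n(n − 1)].

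With n = 18:

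- e = 1 (all others event-free): 17/18 = 94.4% against 17/17 = 100%, a difference of 1/18 = 5.6 points.
- e = 9: 9/18 = 50.0% against 9/17 = 52.9%, a difference of 2.9 points.

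If there were two or three such deaths and all others were event-free, week-16 irPFS would be 16/18 = 88.9% or 15/18 = 83.3%, against 100% with Day 1 censoring.

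**Step 5. Before the death date the shift reverses.** Take three events before week 8 and the disputed death at week 12. Week-8 irPFS is 15/18 = 83.3% with the death counted and 14/17 = 82.4% with Day 1 censoring. The smaller risk set lowers the early part of the curve slightly, and the curve is raised only from the death date onward.

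**The case against.** The best defence is that the affected group may be empty. A screening scan is scheduled for everyone, so the conflict needs a participant who departed from the schedule and then died within one particular 8-week interval. The documents show no such case. The analysis is also descriptive, with no hypothesis tests (SAP 4.1), and Kaplan-Meier analysis of rPFS is optional (SAP 8.1.3). All of this stands. It limits the importance of the point but does not reconcile the rules.

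A second defence is that week 16 is inferred, since the text names the second planned assessment without giving weeks. If the screening scan counted as the first, the text would give week 8 and agree with footnote a. However, the protocol places the first of the 8-weekly scans 8 weeks after Cycle 1 Day 1, and Table 2 works with 16-week windows. On the screening-first reading the text would also conflict with row 2 for participants who have a baseline scan but no later one, and rows 1 and 2 would still clash. Some conflict remains either way.

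A reader might infer three stronger claims, none of which the documents support.

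- **That any death without usable scans is exposed.** Footnote a belongs only to the no-baseline row (step 3).
- **That Day 1 censoring always favours the treatment.** The cohorts are non-randomized and no comparison is tested. The curve is raised only from the death date onward (step 5).
- **That each such death is worth 5.6 points.** That figure is a ceiling (step 4).

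**Conclusion.** The inconsistency is real and is in the current SAP, but it is narrow. It affects participants with no baseline tumor assessment who die after week 8 and up to week 16. For them the text and Table 2 row 2 give an event, row 1 with footnote a gives censoring at the start date, and nothing says which row prevails. The week-16 reading of the text rests on counting planned assessments from the first on-study scan.

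The effect on the Cohort 3B irPFS curve from the death date onward is at most 5.6 points for one such death, falling to 2.9 points when nine of the 18 have had an event, assuming no other censoring. The number of such participants is not given and may be zero. This is a minor correction, worth making because the rule as written can discard a known death that the endpoint definition counts.

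**What to change.** In SAP Table 2, footnote a, change 8 weeks to 16 weeks so that it matches the text and row 2. Deaths up to week 16 in participants without a baseline scan then count as events on the death date under all three statements. No change is needed for participants with a baseline scan but no post-baseline scan.

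The cost is one number in a footnote. It should be settled before the irPFS programming is finalized.
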